Outcome Measures	
[Measures that will used to assess the intervention (for feasibility, tolerability, efficacy, safety, comparability, pharmacokinetics/pharmacodynamics, etc.)]
 
To assess the feasibility of recruiting adult, overweight/obese Black women to the proposed study, the percent of eligible overweight/obese black women who were enrolled and retained in the study will be examined and reasons for nonparticipation and attrition will be documented. Participants will also be asked to provide measurements for height/weight, blood pressure, binge eating, and complete several self-report measures.

Study Duration	2 years
Subject Participation Duration	30 hours
Estimated Time to Complete Enrollment	January 2019-July 2021
Statistical Analysis Plans	
[Feasibility will also be determined by calculation of point and interval estimates (95% confidence intervals using sample size methods) of the feasibility parameters (proportion/percentages in terms of eligibility, participation, retention; means/medians for attendance at intervention sessions) and bivariate frequency distributions. Linear mixed effects modeling will be used to predict the association between treatment group assignment (AAT + NUTR or control), and binge eating, dietary intake, and weight scores at T2 and T3. Baseline scores will be used as

	covariates in these analyses. Standardized mean differences (e.g., Cohen's d with bias adjustment) will also be calculated as an effect size measure with 95% CI.
--	---

2. Introduction: Background and Scientific Rationale

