2.3. Scientific Rationale

[Describe and justify the selected intervention (including dosage, timing, schedule, method of administration, validity of scales, as applicable) and study population.]

Currently, 55% of Black women are obese. Obesity is a serious health problem with numerous co-morbidities. Recent evidence has encouraged investigators to focus their efforts on weight gain prevention in Black women. Consuming a healthy, energy-balanced diet and engaging in physical activity are important for prevention of weight gain. Black women, however, may be vulnerable to certain eating behaviors that may pose barriers to weight management. One particular barrier is binge eating, which is associated with severe obesity. By reducing binge eating episodes in black women, weight gain may be prevented. Based on our analysis, we determined that a sample of 60, evenly allocated between treated and control groups, is sufficiently powered (.80) to identify large standardized mean differences in binge eating ($d = .74$) (Aim #2). The sample, however, is underpowered to determine differences in weight. Because this study is exploratory, we are prioritizing feasibility, and an exploration of differences, rather than determining efficacy.

3. Objectives

The overarching goal of this research to examine the feasibility and acceptability of a combined AAT and NUTR intervention (N=48) in the primary care setting. Participants will be recruited from the UNC Department of Family Medicine, and will be randomized to a group-based 16-week intervention (8 weeks AAT + 8 weeks NUTR) or wait-list control. Following the end of the intervention, I will conduct semi-structured interviews with participants and primary care providers to determine the acceptability of the program.

3.1. Specific Aim 1

Examine the feasibility and acceptability of a 6-month AAT + NUTR (N=48) intervention. AA women (BMI ≥ 25 kg/m²) with weekly binge eating episodes will be randomized to the AAT+NUTR (n=24) or wait-list control (n=24). The study will examine recruitment, retention, barriers to completion, satisfaction, and adherence.

3.2. Specific Aim 2

4. At 4 (end of treatment) and 6 months (follow-up), examine changes in (a) binge eating; (b) depressive symptoms; (c) dietary outcomes (e.g., overall energy intake, fat, fruit and vegetable intake); and (d) weight for participants in each group.

5. Study Design

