9.2. Outcome Measures for Evaluation of Efficacy

Linear mixed effects modeling will be used to examine the association between treatment group assignment (AAT + BWL or wait-list control group coded as a (0,1)-indicator) and binge eating, eating self-efficacy, depressive symptoms, weight, blood pressure, and waist circumference scores at 2 and 6 months. Baseline scores will be used as covariates in these analyses with interactions between treatment group assignments with baseline values of outcome scores. Standardized mean differences (e.g., Cohen's d with bias adjustment) will also be calculated as an effect size measure with 95% CI. Standardized residuals will be examined to assure no assumptions are violated.

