At 4 and 6 months, compare changes in (a) binge eating, eating self-efficacy, and depressive symptoms and (b) weight for participants in the AAT vs. control group. Linear mixed effects modeling will be used to examine the association between treatment group assignment (AAT + BWL or wait-list control group coded as a (0,1)-indicator) and binge eating, eating self-efficacy, depressive symptoms, weight, blood pressure, and waist circumference scores at 2 and 6 months. Baseline scores will be used as covariates in these analyses with interactions between treatment group assignments with baseline values of outcome scores. Standardized mean differences (e.g., Cohen's d with bias adjustment) will also be calculated as an effect size measure with 95% CI. Standardized residuals will be examined to assure no assumptions are violated.

Plans for Aim 3: N/A

Plans for Aim 4: N/A

10.4.Planned Interim Analyses (If Applicable)

N/A

10.5.Plans for Coping with Withdrawals and Loss-To-Follow-Up

Enrolled participants who discontinue/are withdrawn will not be replaced. The initial target number of enrolled participants is large enough to cope with loss of participants' data due to discontinuation, withdrawal, or insufficiently complete data (missing values).

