10.6. Sample Size Rationale

Because this is a feasibility study, we are not prioritizing powering the sample to determine the efficacy of the AAT intervention. However, we ran conservative tests for statistical power incorporating parameters from our preliminary study using G*Power. Based on our analysis, we determined that a sample of 60, evenly allocated between treated and control groups, is sufficiently powered (.80) to identify large standardized mean differences in binge eating ($d = .74$) (Aim #2). The sample, however, is underpowered to determine differences in weight. Because this study is exploratory, we are prioritizing feasibility, and an exploration of differences, rather than determining efficacy. This is a pilot study, If this pilot study is successful, we will conduct a larger study with a greater sample of participants and test the AAT intervention for a longer duration.

11. Safety Monitoring and Management

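### The Aim 2 effect size is not tied to the baseline-adjusted model; computed as an ordinary Cohen's d, it would be needlessly imprecise for stable outcomes such as weight

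*Combined protocol and SAP*

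**What the plan says.** Section 10.3 (Plans for Aim 2) opens with the comparison: "At 4 and 6 months, compare changes in (a) binge eating, eating self-efficacy, and depressive symptoms and (b) weight". It specifies a linear mixed model and states: "Baseline scores will be used as covariates in these analyses with interactions between treatment group assignments with baseline values of outcome scores". It then adds the effect size: "Standardized mean differences (e.g., Cohen's d with bias adjustment) will also be calculated as an effect size measure with 95% CI".

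Section 9.2 has the same sentence ("will also be calculated as an effect size measure with 95% CI"). In the synopsis it directly follows the mention of baseline covariates ("covariates in these analyses. Standardized mean differences"), and the interaction is not mentioned there. None of the three places names the numerator, the SD or the interval method.

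The only numerical effect size is in section 10.6. There "a sample of 60, evenly allocated between treated and control groups, is sufficiently powered (.80") for "large standardized mean differences in binge eating ($d = .74$) (Aim #2"). The same section says that the sample is too small for differences in weight. It gives no SD for weight and no correlation between baseline and follow-up for any outcome.

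**The concern.** The model uses the baseline score. The effect size is an additional output, and the example named, Cohen's d with small-sample correction, is in its usual form the difference between two raw means over their pooled SD. An analyst who follows the text could reasonably compute that.

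For an outcome that hardly changes rank over 4 to 6 months, the raw difference at follow-up consists largely of whatever imbalance randomization left at baseline. The report could then give two figures for one comparison that differ in size or even in sign.

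This matters because section 10.6 describes the study as an exploration of differences ahead of a larger trial, and section 10.1 plays down p-values. Readers will look to estimates and intervals. Weight, where the plan concedes low power, is where ignoring the baseline is likely to cost most.

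**Working it through.** **Inputs.** 30 per arm (60 in total) and d = .74 come from section 10.6. 24 per arm comes from section 3.1 ("will be randomized to the AAT+NUTR (n=24) or wait-list control (n=24"). Two-sided alpha of .05 is assumed because the plan states none. The correlation r between baseline and follow-up is also assumed, with a range of .5 to .98.

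**1. The plan's own figure.** Two-sample t-test, 30 per arm: noncentrality .74 × sqrt(30/2) = 2.87 on 58 df, power .805. The stated .80 is reproduced, with no gain from a baseline covariate. With 24 per arm the power is .71.

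**2. Ordinary d on follow-up means.** SE = sqrt(2/n + d²/(4n)). At d = 0 and n = 30 this is sqrt(.0667) = .258, so the 95% half-width is 1.96 × .258 = .51.

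**3. Baseline-adjusted d on the same SD scale.** SE = sqrt[ (2(1−r²)/n) × (1 + 1/(2n−4)) + d²/(4n) ]. At d = 0 and n = 30:

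| r (assumed) | 1/sqrt(1−r²) | Adjusted half-width | Width ratio, raw to adjusted |
|---|---|---|---|
| .5 | 1.15 | .44 | 1.14 |
| .7 | 1.40 | .37 | 1.39 |
| .9 | 2.29 | .22 | 2.27 |
| .97 | 4.11 | .12 | 4.08 |
| .98 | 5.03 | .10 | 4.98 |

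Simulation at r = .97 gives a ratio of 4.0, with or without the treatment-by-baseline interaction. With 24 per arm the raw half-width is .57 and the ratios hardly change.

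**4. Large d.** At d = .74, r = .97, n = 30 the raw variance is .0667 + .0046 = .0712 (SE .267). The adjusted variance is .0040 + .0046 = .0086 (SE .093). The ratio is 2.9, because error in the SD does not shrink with r.

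**5. Carry-over of imbalance.** The baseline standardized difference has SD sqrt(2/n) = .258 (n = 30) or .289 (n = 24). It exceeds .3 in absolute value in 25% or 30% of trials. About r times it passes into the raw d, so .97 × .3 = .29. With a true effect of −.1, the raw d is then expected near −.1 + .29 = +.19. In simulation (30 per arm, r = .97, true d = .1) the sampling SD was about .26 raw and .065 adjusted. The two estimates had opposite signs in about 35% of trials.

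**6. Change-score d.** On the same SD scale its SE is sqrt(2/(1+r)) times the adjusted one: 1.15 at r = .5, 1.03 at .9, 1.01 at .97. If the divisor were instead the SD of change, which is sqrt(2(1−r)) times the raw SD (1.0, .45 and .24 at those r), the same difference in kg would give a d about 2.2 times larger at r = .9 and 4.1 times larger at r = .97.

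**7. Coverage of 95% intervals (simulation, 30 per arm).** The raw d covers about 95%. For the adjusted d with the model SE alone, coverage is about 95% at d = .1 but 82% at d = .74, r = .97. Adding d²/(4n) to the squared standardized SE restores about 95%.

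**The case against.** The strongest reply is that the plan never commits to a raw d. Cohen's d is given only as an example, and the word *also* shows an extra output without saying that it comes from unadjusted means. The Aim 2 text speaks of comparing changes, and a change-score d loses almost nothing at the high r where the raw d does worst. A model-based d fits the wording too. This stands: a reader might infer that an unadjusted d is planned, and the documents do not establish it. They do not exclude it either, and step 6 shows that under the change-score reading the unnamed SD still moves d severalfold.

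A reader might also infer that the intervals are wrong, or that four times is a typical or limiting figure. Neither holds. The raw interval is inefficient, but its coverage is right. The ratio depends on an r that the documents do not give: it is below 1.7 for r of .8 or less, and above 4 at r = .98.

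Finally, the mixed model is the Aim 2 analysis and does use the baseline. Aim 2 is secondary to feasibility, and no decision rule depends on d. That limits the stakes, but it does not make an undefined effect size acceptable when defining it costs so little.

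**Conclusion.** The point holds in conditional form. The effect size is not linked to the adjusted model, and its means, SD and interval method are undefined. If it is computed as ordinary Cohen's d on follow-up means, precision is lost by the factors in the table: slight for outcomes with moderate r, and two- to fivefold for r between .9 and .98 when the effect is small. High r is plausible for weight and waist over 4 to 6 months, but this is an assumption. For such outcomes and a small true effect, disagreement in sign with the model estimate would be common. At large effects the width ratio is lower (2.9 at d = .74, r = .97) and sign disagreement is rare.

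The power calculation and the primary feasibility aim are unaffected. The change is worth making before analysis.

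**What to change.** In section 9.2, section 10.3 (Plans for Aim 2) and the synopsis, define the standardized difference as follows:

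- **Numerator:** the model's arm difference at each follow-up visit, evaluated at the mean baseline value. The interaction makes this necessary, because without a stated baseline value the model has no single arm difference.
- **Divisor:** the pooled baseline SD, with Hedges correction. Other SDs are defensible; what matters is that one is named.
- **Interval:** a 95% CI that includes sampling error in the SD, either by the delta method (adding about d²/(4n), n per arm, to the squared standardized model SE) or by bootstrap. The model SE alone is not enough.
- **Weight:** also report the adjusted difference in kg with its model CI.

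The cost is a few sentences of text and slightly more analysis work, with no new data. The resulting d is less directly comparable with published raw d values. If that comparison is wanted, the raw d can be given as a labelled supplement.

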10.6. Sample Size Rationale

Because this is a feasibility study, we are not prioritizing powering the sample to determine the efficacy of the AAT intervention. However, we ran conservative tests for statistical power incorporating parameters from our preliminary study using G*Power. Based on our analysis, we determined that a sample of 60, evenly allocated between treated and control groups, is sufficiently powered (.80) to identify large standardized mean differences in binge eating ($d = .74$) (Aim #2). The sample, however, is underpowered to determine differences in weight. Because this study is exploratory, we are prioritizing feasibility, and an exploration of differences, rather than determining efficacy. This is a pilot study, If this pilot study is successful, we will conduct a larger study with a greater sample of participants and test the AAT intervention for a longer duration.

11. Safety Monitoring and Management

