Study Title	Reducing Binge Eating to Prevent Weight Gain in Black Women
Objectives	
Primary: Examine the feasibility and acceptability of a 6-month AAT + NUTR (N=48) intervention. AA women (BMI ≥ 25 kg/m²) with weekly binge eating episodes will be randomized to the AAT+NUTR (n=24) or wait-list control (n=24). The study will examine recruitment, retention, barriers to completion, satisfaction, and adherence.
 
Secondary: At 4 (end of treatment) and 6 months (follow-up), examine changes in (a) binge eating; (b) depressive symptoms; (c) dietary outcomes (e.g., overall energy intake, fat, fruit and vegetable intake); and (d) weight for participants in each group.
 
Tertiary/Exploratory: Conduct key informant interviews (n=15-20) with UNC Department of Family Medicine staff and participants to determine acceptability of the AAT intervention in the primary care setting.

Target Population	
Key Inclusion Criteria Individuals are eligible if they are non-Latino Black women, over 18 years of age, have a BMI ≥ 25kg/m², use a Bluetooth-enabled smartphone, report at least one binge eating episode weekly, and complete the screening.
 
Key Exclusion Criteria Individuals will be excluded if they are currently pregnant, in substance use treatment, involved in a weight loss program, have a history of anorexia nervosa, engage in purging, are currently receiving psychological or pharmacological treatment for disordered eating or eating disorders, or are concurrent intravenous drug users or consume >4 alcoholic beverages/day.

Numbers of Participants	
Number to be recruited for screening [some will not be eligible for enrollment] 200
 
Number of eligible participants enrolled [this is the target sample size for enrollment] 60

Clinical Phase	[I, II, III, or IV (if applicable)]

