The proposed study will use a randomized controlled clinical trial design. A sample of 60 black women who report at least weekly binge eating episodes will be randomized to 2 arms of a 6-month AAT + BWL intervention: AAT+BWL or a control group. AAT+BWL participants will receive an 8-week AAT program, and an 8-week BWL program, both using a group format. Assessments will be conducted at 0, 4, and 6 months. This study will be conducted at one site: UNC Department of Family Medicine.

The goal of AAT is to enable participants to be able to relearn their stomach's hunger signals and begin to obey and monitor functions of satiety 11. AAT has been successful in helping participants diagnosed with Binge Eating Disorder (BED) and bulimia nervosa reduce binge eating, overeating, urges to eat in response to non-appetite stimuli, and prevent weight gain. 12-14 The AAT intervention includes eight 60-minute group sessions. All sessions involve didactic training, review of self-monitoring of eating episodes, interactive activities, and homework assignments to enable participants to practice learned skills. Participants will be provided a workbook, which will include session content, and self-monitoring forms.

The curriculum for BWL (behavioral weight loss) will be based on the evidenced-based curriculum from the Diabetes Prevention Program, or Prevent T2. Eight weekly session will review core content including healthy eating, increasing physical activity, and caloric balance. An outline of session curriculum is attached to the protocol.

[figure not shown]
Physical measures will be taken by trained staff, who will be supervised by [name], PI of this project. The following equipment will be used:

- 1. Height /Weight** will be measured on a digital scale and a wall-mounted stadiometer.
- 2. Waist Circumference** will be measured twice with a Gullick II measuring tape.
- 3. Blood pressure** assessment will be measured using an GE Dinamap Procure Auscultatory 400 Multi-Parameter Patient Monitor with the subject in a sitting position after at least a minute rest period.

Questionnaires:

- 1. Eating Disorder Examination (EDE-Q)** is a self-reported questionnaire based on the Eating Disorder Examination.
- 2. Beck Depression Inventory (BDI)24** is a 21-item questionnaire that measures symptoms and attitudes associated with depression.

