5.1. Treatment Design

The proposed study will use a randomized clinical trial design. A sample of 48 Non-Latino, AA women (BMI ≥ 25 kg/m²; rationale: *prior clinical and research experience suggests that AA women within this BMI range are most likely to identify their eating as problematic and engage in a clinical intervention*²⁶) who report at least weekly binge eating episodes will be randomized to 2 arms of a 6-month intervention: **AAT + NUTR** or **wait-list control**. **AAT + NUTR** participants (n=24) will first receive a weekly, group-based AAT program for the first two months, and then will begin NUTR and receive weekly, group sessions for the next 2 months. **Wait-list control group** (n=24) participants will receive an abbreviated AAT treatment at the end of 6 months. Following the intervention, UNC WMP providers (e.g., social workers, preventive medicine residents), and participants will be asked to participate in a 30-60 minute interview on the acceptability of the AAT +NUTR program, and to explore factors that will increase dissemination and uptake in the primary care setting.

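### The protocol randomises both 48 and 60 women and gives two screening targets (200 and 160); the .80 power belongs to 60 only, and no loss allowance is stated

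*Combined protocol and SAP*

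**What the plan says.** **Number to be randomised.** Section 5.1 plans "A sample of 48 Non-Latino, AA women" and says that those "who report at least weekly binge eating episodes will be randomized to 2 arms of a 6-month intervention". The Synopsis objective and Section 3.1 give the same total as 24 per arm, and Section 3 refers to a "combined AAT and NUTR intervention (N=48) in the primary care setting". By contrast, Sections 5 and 5.2 each state: "A sample of 60 black women who report at least weekly binge eating episodes will be randomized to 2 arms".

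**Enrolment and screening.** The Synopsis enrolment field is annotated "this is the target sample size for enrollment] 60", and Section 6.1 also gives 60. The number to be screened is 200 in the Synopsis and 160 in 6.1.

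**Power.** Sections 2.3 and 10.6 both say that "a sample of 60, evenly allocated between treated and control groups, is sufficiently powered (.80) to identify large standardized mean differences in binge eating", with d = .74. Section 10.6 says that G*Power was used with parameters from the preliminary study. It does not state the test, alpha, sidedness or any loss rate. No power is given for 48.

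**Loss.** Section 10.5 says that participants who leave are not replaced and that the enrolment target is large enough to absorb lost data. It gives no figure. The only retention figure in the document is the pilot's 88% in Section 2.2, which the sample size text does not use.

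**The concern.** Two different totals are each described as the number that will be randomised, so a reader cannot tell which trial is planned. This bears on the primary aim. Recruitment and retention are primary feasibility measures, and Table 2 in Section 5.4 counts women screened and eligible. With two trial sizes and two screening targets, there is no single recruitment target to judge the result against.

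The power statement is a secondary matter. It is tied to 60, so if 48 are randomised it may describe a different trial. If 60 is also exactly the number the calculation needs at analysis, nothing is left for loss, and the assurance in 10.5 has no stated basis.

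**Working it through.** **1. Inputs.** From 2.3 and 10.6: d = .74, power .80, N = 60, equal allocation. From the Synopsis, 3.1 and 5.1: N = 48. From 2.2: pilot retention 88%. Assumed, because not stated: unadjusted two-sample t-test, two-sided alpha 0.05.

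**2. Formula.** With n1 and n2 analysed, power is the probability that a noncentral t variable exceeds the two-sided 5% critical value in absolute size, with n1 + n2 − 2 degrees of freedom and noncentrality d × √(n1·n2/(n1 + n2)).

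**3. The plan's own figure.** For 30 per arm the noncentrality is .74 × √15 = 2.87 on 58 df, and power is 0.805. Solving for .80 gives 29.66 per arm, which rounds up to 30 per arm, or 60. The stated figure is reproduced, and 60 is the number needed at analysis.

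**4. Other numbers analysed, same assumptions.**

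| Analysed | Origin | Power at d = .74 | d detectable with 80% power |
|---|---|---|---|
| 60 (30/30) | 60, no loss | 0.805 | 0.74 |
| 58 (29/29) | 60, two lost | 0.791 | 0.75 |
| 53 (27/26) | 60 × 0.88 = 52.8 | 0.75 | 0.78 |
| 48 (24/24) | 48, no loss | 0.71 | 0.83 |
| 42 (21/21) | 48 × 0.88 = 42.2 | 0.65 | 0.89 |

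The 88% is itself an assumption for this trial: Section 2.2 reports the pilot's binge-eating result at 8 weeks and does not say when retention was measured, whereas follow-up here is 6 months. Over a loss of 5% to 30%, power runs from 0.784 to 0.648 starting from 60, and from 0.686 to 0.548 starting from 48.

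**5. Unstated readings that reach .80 with fewer than 60 analysed.**

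- One-sided 5%: 60 analysed gives 0.88, which does not match the stated .80. With 47 analysed (24/23), power is 0.803. That would require an unstated allowance leaving 47/60 = 78%.
- Baseline adjustment, simple ANCOVA with one follow-up: replace d by d/√(1 − r²) and lose one df. With 24 per arm, r = 0.44 gives 0.798 and r = 0.45 gives 0.802. No correlation is stated.

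**6. Can 48 and 60 be reconciled?** 48 is 80% of 60, so 48 might have been meant as completers. The text does not allow this: the Synopsis objective, 3.1 and 5.1 attach 48 to randomisation. Nor can 60 be enrolled and 48 randomised, because Sections 5 and 5.2 randomise 60.

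**7. Screening.** Pairing each screening field with the 60 enrolled beside it gives planned yields of 60/200 = 30% and 60/160 = 37.5%. With 48, they would be 48/200 = 24% and 48/160 = 30%.

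**8. Effect on the retention estimate.** The Wilson 95% interval is 78% to 94% for 53/60 and 75% to 94% for 42/48, so precision hardly depends on which number is used.

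**The case against.** The strongest reply is that the weight of the text is on 60. Both enrolment fields, Sections 5 and 5.2, and both power statements use it, while 48 appears in the objectives and in 5.1. The power sentence is sound for 60, and 10.6 says that efficacy power is not the priority. This makes 60 the likelier intention and keeps the power point secondary. It does not remove the conflict, since 3.1 and 5.1 are operative design text.

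A second reply is that the yields of 30% and 37.5% use all women screened as denominator, whereas the proportion in Table 2 uses eligible women, and no success criterion depends on either. That is correct. The yields only show that the planned recruitment effort differs; they are not an outcome of the trial.

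A third is that the power figures rest on assumptions. This also stands. The ANCOVA threshold in particular is not derived for the planned mixed model, which has treatment-by-baseline interactions and more than one follow-up time. The remedy is for the sponsor to state what was entered in G*Power.

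Finally, 10.5 promises that the target can cope with lost data, not that power stays at .80. Imputation (10.2) and sensitivity analyses (10.1) are planned. Neither supplies a loss allowance, so the assurance remains unsupported as written.

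**Conclusion.** The concern holds. The current text gives two numbers to be randomised and two screening targets, and no reading of the wording reconciles the two numbers to be randomised. That part needs no assumption.

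The statement of .80 power at d = .74 is correct for 60 analysed under an unadjusted two-sided 0.05 t-test, with essentially no reserve. Under that reading it does not describe a trial of 48, where power is 0.71 even without loss. A one-sided test or a baseline correlation of about 0.45 could change this, but neither is stated. The claim in 10.5 has no loss allowance behind it.

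This should be fixed. The consequence for power is limited by the declared feasibility purpose, and the effect on retention precision is small.

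**What to change.** - Use one number to be randomised and one screening target in the Synopsis, 2.3, 3, 3.1, 5, 5.1, 5.2, 6.1 and 10.6. Which to use is the sponsor's choice.
- In 2.3 and 10.6, state the test, alpha, sidedness and any loss or baseline-correlation assumption entered in G*Power, and restate the power for the chosen number.
- If the two-sided unadjusted test was used and 60 is kept: 60 analysed gives 80% power at d = .74, and 53 analysed (88% retention) gives 75%. If 48 is kept: 48 analysed gives 71% (detectable d 0.83), and 42 analysed (88% retention) gives 65%. A range of loss rates, as in the working, would be better than 88% alone.
- If a one-sided test or a baseline adjustment was used, report that assumption and its power instead.
- In 10.5, state the loss allowance that was used, or delete the sentence saying that the target is large enough.

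The cost is wording only; no extra participants are asked for. Under the two-sided unadjusted reading the stated power becomes less favourable: from 80% to about 75% at 88% retention if 60 are enrolled, or to 71% without loss and about 65% at 88% retention if 48 are.
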